#### Overall Rationale for the Amendment:

Bayer has decided to close all clinical studies with vilaprisan, which were put on temporary pause in December 2018 (protocol amendment 4, Version 4.0) while pre-clinical toxicology findings and their relevance to humans were being further investigated. Although the outcome of Bayer’s investigation revealed that the observed pre-clinical findings are regarded to be of limited relevance to the human situation (refer to IB version 11.0 and Introduction section), a

comprehensive safety follow up will be conducted to provide additional confirmatory evidence. This amendment introduces measures and processes to prepare this study for an orderly closure, including safety follow up measures in all study subjects who received at least one dose of study drug.

### 15.3.1 Overview of the changes

3 Introduction	Information on carcinogenicity studies with vilaprisan in rodents as well as details regarding the additional safety measures were added to the section, included adrenal monitoring, endometrial monitoring, added the new benefit-risk assessment	Provision of comprehensive information about recent events  To re-assess benefits/risks, including the findings from the carcinogenicity studies into consideration and address the newly introduced monitoring
4. Study objectives	Added additional focus on safety evaluations of the endometrium, adrenal glands and skin	To address FDA requests
5. Study design	Updated study design; information deleted	To address FDA requests  With the implementation of this amendment (protocol amendment 5, Version 5.0) no new subjects will be recruited and no study medication will be given to the subjects who have been enrolled in the study
6 Study population 7. Treatments 8. Non-study therapy 9.3 Population characteristics 9.4 Efficacy 9.5 Pharmacokinetics	Updated based on new study design; information deleted	To address FDA requests

cs/pharmacodynamics 11. Data handling and quality assurance		
9.1 Tabular schedule of evaluations 9.2 Visit description	Irrelevant information deleted that is no longer relevant; added “Safety closeout visit” and “Safety result reporting visit”	To depict the procedures of the “Safety closeout visit” and the “Safety result reporting visit”
9.6.1.1 Definition	New criteria for SAE reporting for endometrial biopsies, adrenal tumors, and malignant skin tumors	To address FDA requests
9.6.1.6 AEs of special interest	New AESIs added for adrenal and skin disorders.	To address FDA requests
9.6.3 Further safety	Deleted “In addition, the subjects should be reminded regularly to contact the study site immediately, if they are concerned about such symptoms and testing for unscheduled liver parameters should be considered.”	No longer required as no further treatment will be administered
9.6.3.1 Laboratory evaluations	Added more details on laboratory parameters associated with adrenal disorders. Added requirement for Vit D measurement	To address FDA requirement on adrenal monitoring; Vit D measurement for harmonization of data across all studies
9.6.3.2 Endometrial biopsies	Added more details on endometrial biopsies	To address FDA requests
9.6.3.3 Cervical smear 9.6.3.4 Physical and gynecological examinations 9.6.3.5 Vital signs, weight, and height 9.6.3.6	Revised to reflect the collection of the parameters at the Safety closeout visit.	Update necessary due to new visit structure

Ultrasound (safety)
 
9.6.3.7 Contraception and pregnancy test
		

9.6.3.8 Adrenal monitoring
	
Added description for adrenal monitoring (MRI, laboratory investigations and inquiry)
	
To address FDA requests

9.6.3.9 Liver monitoring
	
Content shifted from previous Section 9.6.1.6 and added alkaline phosphatase (AP) value increasing to > 2x ULN in cases with normal baseline AP as a close observation criterion
	
To address FDA requests

9.6.3.11 Skin monitoring
	
New section added on skin monitoring
	
To address FDA requests

9.7.2 Algorithm for monitoring of endometrial safety
 
9.7.3 Heavy menstrual bleeding / suspicious bleeding pattern
 
9.7.4 Unscheduled endometrial biopsy
	
Content shifted to Sections 9.6.3.2.1, 9.6.3.2.7, and 9.6.3.2.8
	
To address FDA requests

10.2 Analysis sets
	
Adapted FAS and PPS definitions
	
FAS needed to be newly defined to take the handling of subjects into account who were not allowed to start TP1 due to the clinical hold.
 
PPS needed to be newly defined in order to account for the changed analysis (only evaluation of Treatment Period 1).

10.3.1.1 Primary
	
Changed text since primary efficacy analysis will only be performed for
	
Data for Treatment Period 2 is not sufficient to draw

efficacy variable	Treatment Period 1	valid conclusions.
10.3.1.6 Other safety variables	Added adrenal monitoring and skin safety	To address FDA requests
10.3.2.2 Efficacy analysis	Changed text and hypothesis since primary efficacy analysis will only be performed for Treatment Period 1	Data for Treatment Period 2 is not sufficient to draw valid conclusions.
10.4 Sample size	Added text to clarify that the sample size calculation described is not valid anymore.	No new subjects will be included in the study.
10.5 Planned interim analysis	Added text on additional analysis planned before the end of the study	Added to reflect new analysis strategy

#### 15.4 Amendment 6 - dated 17 FEB 2020

Amendment 6 is presented using the same approach as Amendment 5. The rationale for this amendment and all affected sections are provided in the “Protocol Amendment Summary of Changes Table” directly before the Table of Contents in this document. Changes are made directly in the protocol body without annotations. A separate file with tracked changes against the last integrated protocol version is available upon request.

## 16. Appendices

### 16.1 Strong CYP3A4 inhibitors

**Table 16–1: Strong CYP3A4 inhibitors**

Substance name	Inhibitor strength
Boceprevir	Strong
Clarithromycin	Strong
Cobicistat	Strong
Conivaptan	Strong
Delavirdine	Strong
Grapefruit juice	Depending on dose: Moderate or strong
Idelalisib	Strong
Indinavir	Strong
Itraconazole	Strong
Ketoconazole	Strong
Lopinavir	Strong
Mibefradil	Strong
Miconazole	Strong
Nefazodone	Strong
Nelfinavir	Strong
Posaconazole	Strong
Ritonavir	Strong
Saquinavir	Strong
Telaprevir	Strong
Telithromycin	Strong
Tipranavir	Strong
Troleandomycin	Strong
Voriconazole	Strong

### 16.2 Strong CYP3A4 inducers

**Table 16–2: Strong CYP3A4 inducers**

Substance name	Inducer strength
Phenobarbital	Strong
Avasimibe	Strong
Carbamazepine	Strong
Enzalutamide	Strong
St. Johns Wort (Hypericum)	Strong
Lumacaftor	Strong
Methylphenobarbital	Strong
Mitotane	Strong
Phenytoin	Strong
Rifampicin	Strong
Rifamycin	Strong

M&S plan	Modelling and Simulation plan
NRC	National Research Council
P	Progesterone
PAEC	Progesterone receptor modulator-associated endometrial changes
PGI-C	Patient Global Impression of Change
PGI-S	Patient Global Impression of Severity
pH	Potential of hydrogen
PPS	Per-protocol set
PRO	Patient-reported outcome
RAVE	Electronic data capturing system
RND	Randomization
SAE	Serious adverse event
SAF	Safety analysis set
SAP	Statistical Analysis Plan
SAS	Statistical Analysis Software
SD	Standard deviation
SOC	System organ class
TEAE	Treatment-emergent adverse event
TPx	Treatment Period $x, x = 1,2$
TSH	Thyroid-stimulating hormone
UF-DBD	Uterine Fibroid Daily Bleeding Diary

UF-DSD	Uterine Fibroid Daily Symptom Diary
UFS-QoL	Uterine Fibroid Symptom and Quality of Life Questionnaire
ULN	Upper limit of normal
ULOQ	Upper limit of quantification
WHO (-DD)	World Health Organization (-Drug Dictionary)

1. Introduction

Uterine fibroids are benign tumors originating from smooth muscle cells of the myometrium. The pathophysiology of fibroids is not well understood. Genetic predisposition, exposure to steroid hormones, and growth factors play a role in formation and growth.

Uterine fibroids typically appear and grow during reproductive years, but stabilize or regress after menopause. Therefore, they rarely require treatment after menopause. Clinically, fibroids and associated symptoms are most prominent in the late reproductive years. The most common symptoms of uterine fibroids are heavy menstrual bleeding (HMB) and pelvic discomfort.

Uterine fibroids are the leading cause for hysterectomy. Hysterectomy is the only definitive treatment so far and eliminates the possibility of recurrence. The hysterectomy rate has decreased recently but still accounts for almost three quarters of all fibroid related surgical procedures. Increasingly more women desire to avoid hysterectomy, electing for a uterine preserving procedure, regardless of whether they desire to retain their fertility. The surgical treatment options are numerous, and each carries both the risks for surgery itself, as well as the possibility that the woman may require subsequent surgery as new fibroids often develop over time and become symptomatic.

The development of selective progesterone receptor modulators offers the potential for a novel, well tolerated medical treatment approach for women who are experiencing symptoms caused by their fibroids. Various studies have demonstrated the steroid-dependence of fibroid growth and that progesterone has a critical role.

This clinical study is part of a development program for vilaprisan. The rationale of the study is to assess the efficacy and the safety of vilaprisan in subjects with uterine fibroids.

The statistical analysis plan (SAP) is based on the following study protocol documents:

- Integrated Clinical Study Protocol, version 6.0, dated 17 FEB 2020
- Integrated Clinical Study Protocol, version 5.0, dated 21 NOV 2019
- Global Protocol Amendment, version 4.0, dated 11 DEC 2018
- Integrated Clinical Study Protocol, version 3.0, dated 04 JUL 2018
- Integrated Clinical Study Protocol, version 2.0, dated 15 NOV 2017
- Clinical Study Protocol, version 1.0, dated 01 SEP 2017

2. Study Objectives

The primary objective of this study is to show superiority in treatment of HMB of vilaprisan in subjects with uterine fibroids compared to placebo.

The secondary objectives of this study are to additionally evaluate the efficacy and safety of vilaprisan in subjects with uterine fibroids. With the implementation of Integrated Clinical Study Protocol, version 5.0, additional focus will be put on safety evaluations of the endometrium, adrenal glands and skin.

The other objectives of this study are to evaluate the variability in exposure in relation to the efficacy and safety for vilaprisan and to collect patient-reported outcome (PRO) and clinician-reported outcome data.

3. Study Design

This is a randomized, parallel-group, double-blind, placebo-controlled, multicenter study. The study was conducted in the US, Japan and other countries in Europe.

An overview of the study design before the temporary pause is shown in Figure 3–1.

Figure 3–1: Study design as originally planned prior to Global Protocol Amendment, version 4.0

			Treatment Period 1 (TP1)	Treat- ment break (BR)	Treatment Period 2 (TP2)	
Treatment group A1	Screening	Randomization	Vilaprisan 2 mg	Bleeding episode	Vilaprisan 2 mg	Follow-up
Treatment group B1	Screening	Randomization	Placebo	Bleeding episode	Vilaprisan 2 mg	Follow-up
Treatment group B2	Screening	Randomization	Vilaprisan 2 mg	Bleeding episode	Placebo	Follow-up
Duration	up to120 days		12 weeks	· · · · · · · · · · · · · · · · · · ·	12 weeks	Day 7 to 15 of the 2nd menstrual cycle after EoT

Abbreviations: EoT: End of treatment

The following procedures were implemented prior to the Global Protocol Amendment, version 4.0:

- During the screening period, subjects needed to demonstrate eligibility including the presence of at least 1 uterine fibroid ≥ 30 mm and < 120 mm in largest diameter based on ultrasound, HMB in at least 2 bleeding periods, each with menstrual blood loss (MBL) > 80.00 mL documented by the alkaline hematin (AH) method, and endometrial biopsy results without significant histological disorder.
- Eligible subjects were randomized in 1:1:1 ratio to one of the three treatment groups (A1, B1, or B2) and stratified by country/region (US, Japan and other countries). The time between randomization and start of treatment should not have exceeded 40 days.
- After the end of the final treatment period, subjects were followed up until Day 7 to Day 15 of the 2nd menstrual cycle after end of treatment.

With the implementation of the Global Protocol Amendment, version 4.0, no further subjects were recruited. Patients who were randomized but had not yet started treatment were instructed to not start TP1. Patients already in a treatment period were instructed to complete the current treatment period but to not start a new treatment period. Thus, with the implementation of the Global Protocol Amendment, version 4.0, the originally foreseen study

design outlined in Figure 3–1 is not applicable anymore. With the Integrated Clinical Study Protocol version 5.0 the confirmatory analysis was modified accordingly: The confirmatory analysis (originally including TP1 and TP2) will only be based on results of TP1 as the number of patients who start TP2 is not sufficient for drawing valid conclusions.

All subjects who were randomized and started treatment before the temporary pause were asked to have a comprehensive safety evaluation (with particular focus on endometrial, adrenal and skin safety) performed. This also applies to subjects who have completed or discontinued the study before or during the temporary pause, provided they have taken at least one dose of study medication.

4. General Statistical Considerations

4.1 General Principles

The statistical analysis will be performed using the software package SAS release 9.4 (SAS Institute Inc., Cary, NC, USA).

The following Bayer standards are applied: RD-OI-0119 'Prepare statistical documents and programs', RD-SOP-1107 'Recording and Evaluation of Bleeding Data' together with corresponding Bayer standard SAS macro BCycle (version 6.0). Furthermore, global standards for tables and data displays are available and will be specified in the tables, listings and figures (TLF) specification document, which will be approved in parallel with this SAP.

All variables will be analyzed by descriptive statistical methods according to their data type. The number of data available, mean, standard deviation (SD), minimum, median and maximum will be calculated for metric data as appropriate. The number of significant digits for minimum and maximum will correspond to that of the original data. The mean and median will be rounded to one more decimal place than the original data, and the SD it will be rounded to two more decimal places than the original data. Frequency tables will be generated for categorical data including percentages with 1 decimal place. In general, the data will be presented by treatment group (see Figure 3–1) or by treatment period within treatment group, and overall, that is, based on the total study population of the respective analysis set. Tables, figures and listings will show the treatment groups, A1, B1 and B2. Additionally, for selected variables the treatment of vilaprisan in TP1 of the treatment groups A1 and B2 will be presented also as pooled.

Variables recorded in the electronic case report form (eCRF) and relevant derived variables will be shown in subject data listings, whereby only randomized patients will be included. Data from screening failures will only be shown in the 'Screening failure' listing.

Analyses will be performed based on either visits or time intervals as specified in the respective sections. For visit-based analyses the EoT visit will include also (scheduled or unscheduled) EoT visits for subjects who did not start TP2 for any reason, for example, due to the temporary pause of the studies or due to premature discontinuation at the subject's wish. For time interval-based analyses of efficacy variables (except for fibroid surgeries), including analyses for the treatment break and FUP, analyses for the FUP will be based on data from patients who have started TP2. Data from FUP for patients who did not start TP2 for any reason will be included in the analysis of the break period. For those patients only efficacy-related data up to a theoretical end of the break will be considered (see 'break period' in Section 4.5 for details). In contrast to that, for time interval-based analyses of safety variables

(except for bleeding patterns per 28 or 84 days based on UF-DBD), data from FUP for patient who did not start TP2 for any reason will be included in the analysis of the FUP.

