**Originally, the instructions in Sections 7.1 to 7.4 were the following:**

## **7.1 Treatments to be administered**

Eligible subjects will be randomized to one of the following treatment groups:

A1: vilaprisan (2 mg), 2 treatment periods of 12 weeks, separated by 1 bleeding episode

B1: placebo, 1 treatment period of 12 weeks, and vilaprisan (2 mg), 1 treatment period of 12 weeks, separated by 1 bleeding episode

B2: vilaprisan (2 mg), 1 treatment period of 12 weeks, and placebo, 1 treatment period of 12 weeks, separated by 1 bleeding episode

Randomization will be 1:1:1 and stratified by country/region (US, Japan and other countries) for Treatment Groups A1, B1, and B2.

Each treatment period will consist of 12 weeks (84 days). One tablet (oral) will be taken daily during the treatment periods.

The tablets should be taken at about the same time every day. Exceptions to this rule may occur before visits with PK blood sampling (see Section 9.5.1).

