6.2.3.4 Ultrasound examination related variables

The following variables will be presented by (pooled) treatment group and by Intervals B as well as by post-baseline visit (i.e. Visit 4, Visit 5, Visit 6, EoT visit, FUP visit, safety closeout visit):

- Percent change in the sum of the volume of the 3 largest fibroids compared to baseline (measured by ultrasound). If less than 3 fibroids are present, the volume of the actual number of fibroids will be summed.
- Percentage change in volume of the largest fibroid from baseline (measured by ultrasound)
- Percent change in volume of uterus compared to baseline (measured by ultrasound)
- Percentage of subjects with a reduction of $\geq 25\%$ of the sum of the volume of the 3 largest fibroids compared to baseline (measured by ultrasound). If less than 3 fibroids are present, the volume of the actual number of fibroids will be summed.
- Percentage of subjects with a volume reduction of ≥ 25% of the largest fibroid compared to baseline (measured by ultrasound)
- Percentage of subjects with a reduction of $\geq 25\%$ of uterine volume compared to baseline (measured by ultrasound)

If multiple volume assessments are available for a time period, the smallest volume measurement will be used for the Baseline time period, and the largest volume measurement will be used for any other time periods of Intervals B.

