It consists of 37 items including an 8-item symptom severity scale and 29 health-related quality of life questions comprising 6 subscales: concern, activities, energy/mood, control, self-consciousness, and sexual function which are responded to using a recall period of 3 months. All items are scored on a 5-point Likert scale, ranging from "not at all" to "a very great deal" for symptom severity items and "none of the time" to "all of the time" for the HRQoL items.

Symptom Severity, Activities, Revised Activities, HRQoL subscale scores and revised HRQoL scores are summed respectively and transformed into a 0-100-point scale each. The Symptom Severity scale and the HRQoL subscale scores are inversely related with higher Symptom Severity scores indicating greater symptoms while higher HRQoL subscale scores indicate better HRQoL.

Details can be found in Appendix 4.

For each subscale (including the symptom severity scale), raw scores and transformed scores will be summarized using descriptive statistics within treatment group by visit (Visit 3, Visit 5, EoT visit and FUP visit), as well as the absolute change from baseline. The time course for each subscale (raw scores and transformed scores) by visit and by treatment group will be shown using line plots depicting the mean \pm standard deviation.

Change in CGI-I scores compared to baseline

The Clinical Global Impression (CGI-I) is a widely used single item questionnaire which asks the investigator to describe the subject's overall severity of uterine fibroids symptoms. The verbal response options for CGI-I are:

- None
- Very mild
- Mild
- Moderate
- Severe
- Very severe

Each item will be summarized by a frequency table with the number of observations and percentage for each treatment group. CGI-I is recorded at Visit 3 (baseline), EoT visit and FUP visit. CGI-I assessments will be shown by visit. Graphical displays of scores at the three visits will also be provided.

The change from baseline to EoT visit and FUP visit, respectively, will be analyzed using shift tables.

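### The SAP's single 'EoT visit' row puts end-of-TP1 and end-of-TP2 visits together, so in B1 and B2 it mixes placebo with vilaprisan; CGI-I has no other on-treatment time point

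*SAP*

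**What the plan says.** The pause is what creates two kinds of EoT visit in large numbers. SAP Section 3 records that "Patients already in a treatment period were instructed to complete the current treatment period but to not start a new treatment period". For tables by visit, SAP Section 4.1 then rules: "For visit-based analyses the EoT visit will include also (scheduled or unscheduled) EoT visits for subjects who did not start TP2".

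Two of the three groups change drug between periods (protocol Section 7.1):

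- "B1: placebo, 1 treatment period of 12 weeks, and vilaprisan (2 mg), 1 treatment period of 12 weeks"
- "B2: vilaprisan (2 mg), 1 treatment period of 12 weeks, and placebo, 1 treatment period of 12 weeks"

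The by-visit displays that use the EoT label are:

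- **CGI-I** (SAP 6.2.3.6): "CGI-I is recorded at Visit 3 (baseline), EoT visit and FUP visit". It is tabulated per treatment group and visit, with shift tables from baseline to EoT and to follow-up (FUP).
- **UFS-QoL** (SAP 6.2.3.6): summarised "within treatment group by visit (Visit 3, Visit 5, EoT visit and FUP visit").
- **Fibroid and uterine volume** (SAP 6.2.3.4): shown by Intervals B and also at "Visit 4, Visit 5, Visit 6, EoT visit, FUP visit, safety closeout visit".
- **Vital signs** (SAP 6.4.2.6): by treatment group and visit.

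The opening of SAP 6.2.3 says in general terms that further efficacy variables are shown by treatment period and group, with A1 and B2 pooled for TP1. No section says how that applies to the EoT row.

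**The concern.** In B1, an EoT visit after TP1 follows placebo and an EoT visit after TP2 follows vilaprisan. In B2 it is the other way round. One EoT row for each group therefore averages over both drugs, in proportions set by how many women happened to start TP2 before the pause. In A1 there is no drug mix, but one and two courses are combined.

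Collecting clinician-reported data is a stated objective (protocol Section 4), and CGI-I is the only such instrument named. A reader of its shift table would take the B1 and B2 columns as contrasting treatments, when each column holds both. The SAP guards against this problem elsewhere: Section 6.4.2.4.1 assigns adverse events to the drug of the relevant period because B1 and B2 switch, and Section 6.1.6 shows exposure by study drug. The by-visit rule has no such safeguard.

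**Working it through.** There is no plan figure to reproduce. The check has two parts: which outputs are affected, and how strongly a mixed row distorts a comparison of columns.

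**Which outputs have a single-drug alternative**

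| Output | End-of-TP1 display separate from EoT? | Interval display that separates periods? |
|---|---|---|
| CGI-I | No | No |
| Vital signs by visit | None specified | No |
| UFS-QoL | Yes, Visit 5 | No |
| Fibroid and uterine volume | Yes, Visit 5 | Yes, Intervals B |

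Visit 5 falls at Day 78–84 of TP1. That timing comes from the Amendment 1 schedule (protocol 15.1.2.4), because the current schedule no longer prints it. The same schedule lists no vital signs at Visit 5. Intervals B (SAP Figure 4–1) keep TP1 plus break apart from TP2. For interval-based efficacy, SAP 4.1 keeps women without TP2 in the break. UFS-QoL therefore has a single-drug end-of-TP1 row but no single-drug end-of-TP2 row. Visit 5 can also miss women who stopped early in TP1 and had an EoT visit instead.

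**Size of the distortion**

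Inputs:

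- V and P are the mean end-of-period results on vilaprisan and placebo, and D = V − P.
- f is the share of EoT records that follow TP2. The documents do not give it. It is assumed equal in all groups and shown over a range.
- Period, carry-over and length-of-exposure effects are ignored, and equal numbers are taken per group (1:1:1 randomisation).

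EoT rows:

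- A1 = V
- B1 = (1 − f)P + fV = P + fD
- B2 = (1 − f)V + fP = V − fD

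Contrasts:

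- B2 − B1 = D(1 − 2f)
- A1 − B1 = D(1 − f)
- A1 − B2 = fD
- pooled A1+B2 minus B1 = (V − 0.5fD) − (P + fD) = D(1 − 1.5f)

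| f | B2 − B1 | A1 − B1 | A1 − B2 | Pooled A1+B2 − B1 |
|---|---|---|---|---|
| 0.1 | 0.80D | 0.90D | 0.10D | 0.85D |
| 0.3 | 0.40D | 0.70D | 0.30D | 0.55D |
| 0.5 | 0 | 0.50D | 0.50D | 0.25D |
| 0.75 | −0.50D | 0.25D | 0.75D | −0.125D |

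For illustration, with assumed rates V = 0.7 and P = 0.3 (D = 0.4), the rows are:

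- f = 0.25: A1 0.70, B1 0.40, B2 0.60
- f = 0.5: A1 0.70, B1 0.50, B2 0.50
- f = 0.75: A1 0.70, B1 0.60, B2 0.40

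B1 and B2 are single-drug rows only at f = 0 or f = 1.

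**After a split by last period started**, under the same simplifications, every cell holds one drug. After TP1, A1 and B2 give V and B1 gives P. After TP2, A1 and B1 give V and B2 gives P. Each drug contrast then equals D whatever f is.

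**The case against.** The strongest reply is that SAP 6.2.3 already promises display by treatment period and group, that Section 4.1 allows display by period within group, and that the table specification, which is a separate document, may settle the layout. This stands in part: the SAP may have intended a split. But the EoT rule is the specific one, the CGI-I text prescribes one EoT column per group, and nothing says how EoT is divided. Vital signs lie outside 6.2.3 altogether. At the least, the passages need aligning.

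Four stronger readings are tempting and are not supported:

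- *UFS-QoL and fibroid results as a whole cannot be read by drug.* Visit 5 serves both, and Intervals B serve the volumes. Only their EoT row is unreadable by drug.
- *Before the pause, EoT always followed TP2.* The Amendment 1 schedule already had an EoT visit for women withdrawn during treatment, so some mixing was built in.
- *The women whose EoT followed TP1 give a clean randomised comparison.* They did not start TP2 for any reason, so the set joins women stopped by the pause with early discontinuers and leaves out everyone who went on to TP2.
- *A planned evaluation of clinician-reported outcomes fails.* The protocol objective is only to collect these data, and no between-group CGI-I test is planned.

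It is also fair to say that f may be small, since SAP Section 3 states that too few women started TP2 for valid conclusions. At f = 0.1, B2 − B1 still keeps 80% of D. Subject listings would also allow later reclassification.

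**Conclusion.** The point holds in a limited form. The Section 4.1 rule yields an EoT row that cannot be attributed to a drug in B1 and B2. The consequence is full for CGI-I and applies to vital signs by visit. For UFS-QoL and ultrasound it is confined to the EoT row. By-visit FUP rows may have the same fault, because the last drug taken in B1 and B2 depends on whether TP2 was started, and the SAP does not say how non-starters' FUP visits are handled in those tables.

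The distortion of B2 − B1 is the factor (1 − 2f). It is illustrative only, because f is unknown and the formula assumes equal f across groups and no period or carry-over effects. Every affected analysis is descriptive. The four confirmatory tests use TP1 data and are not touched. The change should be made, but it does not bear on whether the trial succeeds.

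**What to change.** 1. In SAP 4.1, replace the single EoT label with two analysis visits, 'EoT after TP1' (TP2 not started) and 'EoT after TP2', assigned by the last treatment period started. Label by-visit FUP rows in the same way.
2. Apply this to CGI-I, UFS-QoL, ultrasound by visit and vital signs, and align SAP 6.2.3.6 with the general display sentence in 6.2.3.
3. Show pooled A1+B2 only for 'EoT after TP1'. Describe it as a single-drug comparison in a selected subset, and ideally distinguish women stopped by the pause from early discontinuers.

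The cost is SAP wording and one derived visit variable. No new data are needed. The downside is fewer women per row.
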